| Diagnosis and Main Inclusion Criteria | Depressed adolescent (ages 12-18) participants with moderate to severe major depressive disorder (MDD) defined by a score of 40 or greater on the Children’s Depression Rating Scale, Revised (CDRS-R) and an interview with the Mini International Neuropsychiatric Interview (MINI). |
| Study Device | NeuroStar® TMS Therapy System in XPLOR research configuration |

| | |
|--------------------------------|---|
| 
Duration of Exposure
 | 
Phase I - 6 weeks (30 sessions) and 3 week taper (3 sessions for one week, then 2 sessions for the next week, then 1 session for the last week of the taper). Based on randomization participants will either receive sessions of 1 Hz rTMS at 120 % motor threshold (MT) with 2400 continuous pulses or 10 Hz rTMS at 120 % MT with 4 seconds on and 36 seconds off for 2400 pulses. Both 1 Hz and 10 Hz rTMS sessions will be delivered to the left dorsolateral prefrontal cortex (LDLPFC).
 
Phase II- 2 weeks (10 sessions) of continuous theta burst (cTBS) or intermittent theta burst (iTBS) based on biomarker (ICF) status. Note that TBS sessions involve the delivery of 3 pulses of 50 Hz stimulation given every 200 milliseconds (ms) or 5 Hz. Participants assigned to cTBS will receive 10 daily sessions (5 sessions per week for two weeks) with 120 second trains of uninterrupted TBS for 1800 pulses at 80% MT. Participants assigned to iTBS will receive 10 daily sessions (5 sessions per week for two weeks) with 2 second trains every 10 seconds for a total of 570 seconds for 1800 pulses. Both cTBS and iTBS sessions will be delivered to the LDLPFC.
 
NeuroStar TMS is not an implant. Stimulation is delivered during the daily sessions in the neurostimulation suite.
 |
| 
Reference therapy
 | 
Not Applicable
 |

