1.6 Anticipated Duration of the Clinical Investigation

It is anticipated that the proposed study will be five years in duration. For individual participants, Phase I (biomarker stratified, randomized trial of 1 Hz vs. 10 Hz rTMS) is 10 weeks in duration. Phase II (trial of cTBS vs iTBS based on ICF biomarker status) is 3 weeks in duration.

2 Study Objectives

The proposed study is a dose finding, effectiveness, and target validation study of rTMS for adolescent depression with a biomarker stratified design.⁷² Intracortical facilitation (ICF),⁶⁵ a transcranial magnetic stimulation (TMS) measure of cortical glutamatergic tone is the target engagement biomarker for the proposed trial. In phase I, a cohort of adolescents (ages 12-18) with clinically significant depression defined as 40 or greater on the Children's Depression Rating Scale-Revised (CDRS-R) will be stratified according to baseline ICF (high defined as > 1.5 or low defined ≤ 1.5) and then randomized to 6 weeks of either left prefrontal 1 Hz or 10 Hz rTMS. The research team will collect weekly ICF and CDRS-R measures during treatment. We will assess baseline anhedonia with a composite measure from relevant CDRS-R and Beck Depression Inventory-II (BDI-II) items. We will assess lifetime adversity with the Childhood Trauma Questionnaire (CTQ).

Participants in Phase I will be offered the opportunity to have 3 and 7 T MRI and MRS looking for biomarkers at baseline and after 6 weeks of treatment. A subgroup of depressed adolescent participants (up to 50) who do not respond to 1 Hz or 10 Hz rTMS will be offered the opportunity to participate in an exploratory, 2 week, trial of iTBS or cTBS based on ICF biomarker status (Phase II of the study). Participants with high baseline ICF (defined as > 1.5) will be assigned to cTBS treatment. Participants with low ICF (defined ≤ 1.5) will be assigned to iTBS.

7 T MRS measures Glutamate and GABA biomarkers in healthy adolescents and depressed adolescents. The overall goals are to examine cortical Glutamate and GABA neurochemical markers in adolescent depression and the impact of 1 Hz and 10 Hz rTMS on cortical glutamate and GABA neurochemical markers when compared to the healthy adolescent cohort.

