2.2 Secondary Objective

Aim 2 examines changes in weekly ICF and CDRS-R across 6 weeks of either 1 Hz or 10 Hz rTMS.

- We anticipate that ICF measures will decrease in depressed adolescents receiving 6 weeks of 1 Hz rTMS.
- We anticipate that ICF measures will increase in depressed adolescents receiving 6 weeks of 10 Hz rTMS.

Depressive symptom improvement will have a direct relationship with ICF decrease in depressed adolescents receiving 6 weeks of 1 Hz rTMS and an indirect relationship with ICF increase in depressed adolescents receiving 10 Hz rTMS.

Exploratory Aim 3

Aim 3a: To compare 7 T MRS cortical measures of GABAergic tone and glutamatergic neurochemistry in depressed adolescents and healthy control adolescents.

Aim3b: To examine potential changes in cortical GABAergic and glutamatergic neurochemistry after a six week course of either 1 Hz or 10 Hz rTMS in depressed adolescents.

Hypothesis:

1. Depressed adolescents will have decreased cortical levels of GABA as assessed with 7 T MRS compared to healthy control adolescents.
2. Depressed adolescents will have increased cortical levels of Glutamate as assessed with 7 T MRS compared to healthy control adolescents.
3. Bilateral cortical 7 T MRS measures of GABA will increase after 6 weeks of 1 Hz rTMS in depressed adolescents.
4. Bilateral cortical 7 T MRS measures of Gln/Glu will decrease after 6 weeks of 1 Hz rTMS in depressed adolescents.
5. Bilateral cortical 7 T MRS measures of GABA will decrease after 6 weeks of 10 Hz rTMS in depressed adolescents.

6. Bilateral cortical 7 T MRS measures of Gln/Glu will increase after 6 weeks of 10 Hz rTMS in depressed adolescents.

Exploratory Aim 4 examines clinical moderators of treatment (anhedonia and adversity) in this sample of adolescents undergoing treatment with 1 Hz and 10 Hz rTMS.

Hypothesis:

6 weeks of low frequency (1 Hz) rTMS vs. high frequency (10 Hz) rTMS will have greater efficacy (as assessed by CDRS-R) in depressed adolescents with anhedonia and adversity compared to depressed adolescents without anhedonia and adversity

The proposed project will examine an rTMS dosing, target engagement strategy for adolescent depression and refine understanding of GABAergic and glutamatergic contributions to negative valence. Findings will inform the clinical dissemination of rTMS for adolescent depression and provide insights to further treatment innovation for disorders of the negative valence systems domain early in life.^{9,52}

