3.1 General Design

Phase I will enroll a cohort (N=120) of adolescents (ages 12-18) with clinically significant depression defined as 40 or greater on the Children’s Depression Rating Scale-Revised (CDRS-R). Participants will be stratified according to baseline ICF (high defined as > 1.5 or low defined ≤ 1.5) and then randomized to 6 weeks of either left prefrontal 1 Hz or 10 Hz rTMS. The research team will collect weekly ICF and CDRS-R measures during treatment. We will assess baseline anhedonia with a composite measure from relevant CDRS-R and Beck Depression Inventory-II (BDI-II) items. We will assess lifetime adversity with the Childhood Trauma Questionnaire (CTQ). Participants will have baseline neurocognitive testing. Participants will have a six month follow-up visit with depression severity measures (CDRS-R and BDI-II) and neurocognitive assessments.

Up to 100 Depressed adolescents will be offered the opportunity to undergo magnetic resonance spectroscopy (MRS) measure at baseline (prior to any Phase I TMS treatment) and posttreatment visits (within 2 months after 6 weeks of TMS treatment in Phase I). A comparison group of 30 healthy control adolescents will be offered the opportunity to undergo MRS at one time point. A subset of up to 50 depressed adolescents who do not respond to Phase I TMS treatment will be offered the opportunity to continue in Phase II (within 2 months of completion of Phase I treatment) for two weeks of either iTBS if (ICF ≤ 1.5) or cTBS if (ICF is >1.5).

Magnetic Resonance Imaging: Depressed and control participants will undergo 3 T structural MRI and ultra-high field (7 T) MRS (7-T, 90-cm horizontal bore magnet interfaced with a Siemens console) to examine GABA, glutamate, and glutamine concentrations in the occipital cortex (OCC). [name] is a co-investigator on this grant and will supervise the collection and analyses of all MRI/MRS data at the Center for Magnetic Resonance Research (CMRR) at the University of Minnesota. Please note that travel time from Mayo Clinic Rochester to the CMRR is approximately 1 hour. Participants will be remunerated for travel and all study visits.

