Recent work in adult humans with 7 T MRS and short echo time sequences has enhanced the detection and resolution of GABA, glutamate and glutamine. Spectra will be acquired from a voxel placed in the OCC using the STEAM sequence. Voxels will be prescribed using anatomical landmarks from T1-weighted images. Spectra will be stored separately for subsequent automatic frequency and phase correction (in-house written Matlab routines) using the NAA signal at 2.01 ppm. Summed spectra will be analyzed using LCModel 6.1-4A (Stephen Provencher Inc., Oakville, ON, Canada) and simulated basis sets with a metabolite-nulled macromolecule spectrum measured in vivo. No baseline correction, zero-filling or apodization functions will be applied to the in vivo data prior to the analysis. LCModel fitting will be performed over the spectral range from 0.5 to 4.2 ppm. The quantification will be performed using the unsuppressed water signal obtained from the same voxel. Concentrations will be corrected for cerebrospinal fluid content (the tissue composition will be obtained via voxel segmentation using T1-weighted images acquired at 3 T).

The first MRS will take place following the screening visit but before the baseline/treatment visit occurs. Therefore, a 7 day window is the allowed timeframe for the first MRI and MRS scan. The second MRS will take place within 2 months of completing all rTMS phase I treatments and assessments and before beginning Phase 2 treatments. Screening will include University of Minnesota Center for Magnetic Resonance Research systematic safety assessments for safety to undergo both rTMS and ultra-high field (7 T) MRI/MRS.

Please note that travel time from Mayo Clinic Rochester to the CMRR is approximately 1 hour. Participants will be remunerated \$100.00 per scan for their time and travel expenses.

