5.7 Participant Compliance Monitoring

Non-adherence to the assigned treatment regimen is defined as missing ≥ 3 treatments in daily sequence, or missing more than 20% of the total number of treatment sessions occurring during the 6 weeks of acute treatment (does not include taper treatments) as outlined in the schedule of events (i.e., 100% compliance = 30 total treatments). However, if the participant does miss a treatment, the participant must not go more than 3 calendar days without a treatment session. Treatments missed during the taper visits are considered protocol deviations. Participants who are unable to comply with this schedule may be withdrawn from the investigational treatment portion of the study. If a participant receives more than the prescribed number of pulses (i.e. 2400 pulses of good contact), this would be considered an overdose and documented on the SAE form and reported to the IRB and US FDA.

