| TMS Neurophysiology Measures (MT, SICI, ICF, LICI, CSP) | Single (motor threshold and cortical silent period) and paired-pulse (intracortical facilitation, short-interval cortical inhibition, long-interval cortical inhibition). TMS neurophysiology measures will be collected in depressed adolescent participants at baseline, weekly during six weeks of rTMS treatment with 1Hz or 10 Hz rTMS (phase I), posttreatment, and weekly for 2 weeks for depressed adolescent participants in a, trial of cTBS or iTBS (phase II). |

Table 3 Phase I Assessments

| Phase I | 1-Week Prestudy | | 6-Week Treatment (1 Hz vs. 10 Hz) | | | | | | 3-Week Post-Treatment Taper | | | 6-Month Follow Up |
|---|---|---------------------------------|-----------------------------------|-------------------|-------------------|-------------------|-------------------|-----------------------------|-----------------------------|-------|-------|-------------------|
| | Wk -2 to -1 ^a (Screening) | Wk 0 ^a (Baseline) | Wk 1 ^b | Wk 2 ^b | Wk 3 ^b | Wk 4 ^b | Wk 5 ^b | Wk 6 ^{b,c} /E T | Wk 1 | Wk 2 | Wk 3 | |
| | -7 ^a | 0 ^a | 1-5 | 8-12 | 15-19 | 22-26 | 29-35 | 36-42 | 43-49 | 50-56 | 57-63 | |
| Informed Consent/Assent/HIPAA | X | | | | | | | | | | | |
| CMRR Safety Screen (prior to MRI/MRS) | X | | | | | | | X | | | | |
| UCSD Brief Assessment of Capacity to Consent (UBACC) (only patients age 18 participating in MRI/MRS scans at CMRR) | X | | | | | | | | | | | |
| MRI/MRS Study(Before Baseline Appt.) | X | | | | | | | X | | | | |
| Transcranial Magnetic Stimulation Adult Safety Screen (TASS) | X | | | | | | | | | | | |
| Antidepressant Treatment History Form (ATHF) | X | | | | | | | | | | | |
| Abnormal Involuntary Movement Scale (AIMS) | X | | X | X | X | X | X | X | X | X | X | X |
| MINI / MINI-Kids | X | | | | | | | | | | | |
| CTQ | | X | | | | | | | | | | |
| PDS | | X | | | | | | | | | | |

| Phase I | 1-Week Prestudy | | 6-Week Treatment (1 Hz vs. 10 Hz) | | | | | | 3-Week Post- Treatment Taper | | | 6- Mont h Follo w Up |
|--------------------------------------|---|---------------------------------|--------------------------------------|----------------------|----------------------|----------------------|----------------------|--------------------------------|---------------------------------------|----------------|----------------|----------------------------------|

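### The second MRS scan is timed inconsistently, so the six-week change in exploratory Aim 3b can mix the acute course with taper sessions and time off stimulation

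*Combined protocol and SAP*

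**What the plan says.** Three places time the second scan.

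- **Section 3.1, paragraph offering scans to depressed participants:** it is done at "posttreatment visits (within 2 months after 6 weeks of TMS treatment in Phase I").
- **Section 3.1, imaging paragraphs:** "The second MRS will take place within 2 months of completing all rTMS phase I treatments and assessments and before beginning Phase 2 treatments".
- **Table 3:** the row reads "MRI/MRS Study(Before Baseline Appt.) | X | | | | | | | X". The second mark falls in the Week 6/early termination column. The taper columns are empty and no footnote gives a window.

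The scientific question is tied to the six-week course. A typical Aim 3b hypothesis (Section 2.2) is "Bilateral cortical 7 T MRS measures of GABA will increase after 6 weeks of 1 Hz rTMS in depressed adolescents". Section 7.2 plans mixed models for the change in GABA and Gln/Glu over six weeks, fitted separately in the 1 Hz and 10 Hz arms. It names no term for the date of the scan or the number of sessions received by then.

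Three places bear on whether the taper belongs to Phase I treatment:

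- The Study Summary lists under Phase I exposure a "3 week taper (3 sessions for one week, then 2 sessions for the next week, then 1 session for the last week".
- Section 5.7 states "Treatments missed during the taper visits are considered protocol deviations".
- Section 1.6 states "Phase I (biomarker stratified, randomized trial of 1 Hz vs. 10 Hz rTMS) is 10 weeks in duration".

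**The concern.** The three timings cannot all be followed. A Day 42 scan satisfies Table 3 and the first statement in Section 3.1, but not the imaging paragraph read literally. A Day 120 scan satisfies only the imaging paragraph. Participants scanned under different statements would differ in stimulation received and in time since it stopped, yet share one post-treatment value.

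The within-arm estimate would then average over an unplanned mixture: the effect of the acute course, any effect of the taper, and whatever happens after stimulation ends. The sponsor's earlier spectroscopy study (Section 1.1) makes this relevant. It treated post-treatment and six-month scans as separate time points, and found Gln/Glu inversely related to CDRS-R throughout treatment and follow-up.

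Scan delay may also be related to outcome. The requirement to scan before Phase II limits the date only for non-responders who enter Phase II. Early discontinuers are to complete Week 6 procedures within 2 days of their last session (Section 4.4.1), and the scan sits in that column of Table 3.

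**Working it through.** **1. Does Phase I include the taper?** Screening 1 week + treatment 6 weeks + taper 3 weeks = 10 weeks. This reproduces the duration in Section 1.6; without the taper the sum is 7. The imaging paragraph also requires assessments to be complete, and Table 3 continues the CDRS-R and C-SSRS through the taper. The taper reading is therefore the better supported one.

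**2. Calendar.** Table 3 gives the days for Week 6 and the three taper weeks as "36-42 | 43-49 | 50-56 | 57-63". Six treatment weeks therefore end on Day 42 and the taper on Day 63. Two months is taken as 60 to 62 days (assumption).

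**3. Sessions.** Five sessions a week give 5 × 5 = 25 before Week 6 starts and 30 at its end. The taper adds 3 + 2 + 1 = 6, for a total of 36, and 6/30 = 20% more. These are nominal counts; missed sessions or early stopping would lower them.

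**4. Latest scan day and sessions received under each statement**

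| Source | Latest scan day | Sessions received by the scan |
|---|---|---|
| Table 3 | 42 (earliest 36) | about 25 to 30 |
| Section 3.1, scan-offer paragraph | 42 + 60 to 62 = 102 to 104 | 30 to 36 |
| Section 3.1, imaging paragraph, taper counted | 63 + 60 to 62 = 123 to 125 | 36 |

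**5. Spread.** The smallest gap is 123 − 42 = 81 days and the largest is 125 − 36 = 89 days, that is 11.6 to 12.7 weeks. The course itself is 42 days. The two prose windows end 63 − 42 = 21 days apart.

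**6. If the taper is not counted.** Both prose windows then end near Day 102. Scans could still lie 102 − 42 = 60 to 102 − 36 = 66 days apart, after about 25 to 36 sessions. A Day 102 scan would fall 102 − 63 = 39 days after a Day 63 taper session.

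**The case against.** The strongest reply is that this is loose wording. Table 3 marks a nominal visit and states no window. The two prose windows overlap: a scan from about Day 63 to Day 102 meets both. Table 3 labels the taper as post-treatment, and Section 5.7 separates acute from taper sessions when it defines adherence. If the imaging paragraph means only the 30 acute sessions, the two prose statements largely agree. That ambiguity is fair. It does not remove the problem, because on that reading too the scan can fall in Week 6 or about two months later and still count as one value.

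Three stronger readings are tempting, and the documents do not support them.

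- **A fading effect would be diluted by a calculable amount.** No decay rate is given. The only relevant evidence, in Section 1.1, is that mean Gln/Glu was still raised at six months. That was after 10 Hz, at 3 T and in different voxels (dorsolateral prefrontal and anterior cingulate, not occipital), with GABA not adequately resolved. It establishes neither fading nor persistence for this trial.
- **Unequal delay between arms biases the result.** Section 7.2 plans separate models within each arm and specifies no between-arm MRS contrast, so a delay difference between arms biases no planned comparison.
- **Non-responders are forced into early scans.** Section 3.1 allows the Phase II decision up to 2 months after Taper Week 3, which matches the imaging paragraph's limit. Section 5.3 says 30 days. Those two limits must themselves be reconciled. A link between delay and response is possible, not shown.

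**Conclusion.** The inconsistency is real and stands in the current text. Followed as written, the imaging paragraph measures something other than the six-week change that Aim 3b asks about. Scans 81 to 89 days apart could be analysed as the same value; if the taper is excluded from Phase I treatment, the figure is about 60 to 66 days.

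This rests on the nominal Table 3 calendar and on 60 to 62 days for two months (60 for the narrower reading). The size of any effect on the GABA or Gln/Glu estimates cannot be derived from the documents.

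The consequence is limited. Aim 3 is exploratory, the scans are optional, and no power is claimed for them. The primary CDRS-R endpoint and the secondary ICF endpoint are unaffected, as is the baseline comparison with healthy controls, which uses only the first scan.

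**What to change.** - **Wording.** Give both statements in Section 3.1 and Table 3 the same anchor and window, matched to Aim 3b: after the 30th acute session, and before the first taper session where feasible. State the anchor for participants who stop before session 30.
- **Data.** For every second scan, record days since session 30 and total sessions received.
- **Analysis.** Keep all scans. Add both quantities as covariates in the Section 7.2 models, set to zero at baseline, with sessions coded as the difference from 30. The post-treatment term then estimates the change at session 30. The two will be correlated, because taper sessions accumulate with time, so one term may be enough.
- **Sensitivity.** Report the in-window scans alone. This matters because covariate adjustment may not remove a dependence of delay on response.

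The cost is a wording change, one or two extra model terms and tighter booking. Booking is the real constraint. With Monday starts, the nominal 30th session falls on Day 40 and the taper can begin on Day 43, and the scanner is about an hour away. Some scans will miss the window, but none is discarded from the main analysis.

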3.2 Primary Study Endpoints

The primary study endpoint is depression severity (measured by CDRS-R total) over the 6-week study period.

3.3 Secondary Study Endpoints.

The secondary study endpoint is intracortical facilitation (ICF) over the 6-week study period.

3.4 Table 1 Primary Safety Endpoints

| Assessment | Description |
|---|--|
| Adverse events | Participants will be evaluated for adverse events at each visit. Serious adverse events (SAEs) will be reported as they occur to the Mayo Clinic IRB and USA FDA (as per regulations). Systematic data collection focused on adverse events will include the Pediatric Adverse Event Rating Scale and Physical Symptom Checklist. These rating scales will be administered at baseline, weekly (during all rTMS, cTBS, and iTBS treatment weeks), at the 6 month follow up visit, and at study exit. |
| Auditory thresholds | Participants will undergo audiometry testing at baseline and upon completion of 6 week rTMS (1 Hz or 10 Hz) and once again (if applicable) after the two week open extension trial (of either cTBS or iTBS). |
| C-SSRS – Columbia Suicide Severity Rating Scale | This is collected to assess lifetime suicidal ideation and behavior prior to participation, reassessed weekly (during 6 week trial of 1 Hz vs 10 Hz rTMS and if applicable 2 week extension trial of cTBS or iTBS) during treatments, posttreatment, and 6 month follow up visit. |
| NIH Toolbox Cognition Battery | 
http://www.healthmeasures.net/explore-measurement-systems/nih-toolbox
 
Cognition measures: http://www.healthmeasures.net/explore-measurement-systems/nih-toolbox/intro-to-nih-toolbox/cognition
 
The NIH Toolbox Cognition Battery, recommended for ages 7+, consists of tests of multiple constructs. It yields individual measure scores and the following summary scores: Education, Handedness, Attention (Flanker Inhibitory Control and Attention Test), Episodic memory (Picture Sequence Memory Test, and Auditory Verbal Learning Test), Executive Function (Dimensional Change Card Sort Test, Flanker Inhibitory Control and Attention Test), Language (Picture Vocabulary Test, Oral Reading Recognition Test), Processing Speed (Pattern Comparison Processing Speed Test), Working Memory (List Sorting Working Memory Test). Collected at baseline, posttreatment, and 6 month follow up.
 |
| Pediatric Adverse Event Rating Scale | This is a 51 item; self-report measure collected at baseline, weekly during rTMS treatments, posttreatment, and at 6 month follows up visit for adverse event monitoring. |
| Physical Symptoms Checklist | This is a 46 item measure to be collected by the study team (under the supervision of the PI) at baseline, weekly during rTMS treatments, posttreatment, and at 6 month follow up visit for adverse event monitoring. |

| Assessment | Description |
|-------------------------------|---|
| Vital Signs | (Pulse, blood pressure, height, and weight) will be collected at baseline, upon completion of 6 week rTMS (1 Hz or 10 Hz) once again (if applicable) after two week open extension trial (of either cTBS or iTBS), and at 6 month follow up visit. |
| YMRS-Young Mania Rating Scale | This is an 11 item measure used to assess for manic symptoms. The YMRS scale will be completed at baseline and repeated during the course of study participation if symptoms of mania occur in a study participant. If the YMRS is positive, A MINI/MINI-Kid will be repeated to evaluate for mania. If the study participant meets full DSM-5 criteria for mania or hypomania he or she will be discontinued from the study and followed clinically. |

4 Participant Selection, Enrollment and Withdrawal

